### Tracking and Storage of Samples

#### Disposition of samples:

When initially collected, all specimens should be labeled with the patient's name, hospital number, date and time of collection. Once the samples reach the laboratory they will be appropriately labeled and coded without names. The information on the subjects' names and ID numbers will be kept in a log book in a locked cabinet.

At this time (11/2008) the samples are recorded in a laboratory notebook in [name]. The information includes the patient's name, ID number, date of biopsy and whether the sample is pre- or post-ixabepilone administration. We intend to upgrade the tracking process to an electronic spreadsheet that contains the patient ID, trial name/protocol number, time drawn, cycle time point, dose, material type, as well as box and freezer location. Samples remaining after the study completes will be stored in the same freezer in [name] lab and eventually transferred to [name] core facility for possible future study as outlined below. The study consent contains a section asking patients for permission to keep the tissue for use in research to learn about, prevent, or treat cancer or other health problems.

Material remaining after completion of correlative studies (with the exception of biopsy samples) will be transferred to the laboratory of [name] to be entered into the Clinical Pharmacology Program's "Patient Sample Database Management System" (PSDMS) - Labrador. This is a secure program that can only be accessed by authorized users in [name] lab. PSDMS creates a unique barcode ID for every sample and sample box that cannot be traced back to patients without PSDMS access. These samples will be managed in accordance with the laboratory's policies and procedures.

The data recorded for each sample includes the patient ID, trial name/protocol number, time drawn, cycle time point, dose, material type, as well as box and freezer location. There are patient demographics that can be obtained to correlate with the samples through the PSDMS system. For each samples, there are notes describing the processing method (delay in sample processing, storage conditions on the ward, etc.). Bar-coded samples are stored in bar-coded boxes in a locked freezer at either -20 or -85°C according to stability requirements. These freezers are located onsite in [name] lab and offsite at NCI Frederick Central Repository Services (Fisher Bioservices) in Frederick, MD.

Samples will be stored until requested by the researcher assigned to the protocol (however, those requests must come from a member of [name] laboratory with PSDMS access/clearance). All requests are monitored and tracked in the PSDMS system. All researchers are required to sign a form stating that the samples are only to be used for research purposes associated with this trial (as per the IRB approved protocol – that protocol is stored in the PSDMS system) and that any unused samples must be returned to [name] laboratory.

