- 1) Immunohistochemical staining will be performed using antibodies that as described above can assess the extent of tubulin stabilization (antibodies that detect acetylated alpha-tubulin and detyrosinated (glu-terminated) alpha-tubulin. Specifically we will be looking to see if in the malignant cells, tubulin polymerization occurs following treatment with ixabepilone as evidenced by enhanced staining with the acetylated alpha-tubulin and detyrosinated (glu-terminated) alpha-tubulin antibodies. If there are normal cells in the biopsy (a likely possibility) we will be able to compare the observations in malignant cells with that in normal cells. This will allow us to determine if ixabepilone has reached its target and resulted in tubulin polymerization, by comparing the results in the post-treatment sample with those in the pre-treatment sample. This information will be valuable in analyzing the reasons for treatment failure by discriminating between an absence of an effect on the target (tubulin) versus a lack of subsequent events that leads to cell death. Because both the pre-treatment and post-treatment samples will be in blocks we will be able to easily perform additional studies, including additional immunohistochemical stains. One such stain will utilize an antibody that detects the 85kDa fragment generated when PARP cleavage occurs. We are aware of the use of this antibody in other settings, and in one center, it has been used to examine some tumor samples obtained after the administration of ixabepilone. In one patient with breast adenocarcinoma metastatic to the skin, investigators were able to demonstrate immunostaining with the antibody against 85kDa fragment 24 hours after the administration of ixabepilone. Immunostaining for p53 will also be performed [42].
- 2) RNA, and will be extracted and this will be banked. Its fate will depend on the response rates observed in this trial. If ixabepilone is found to be active in over 20% of patients, then all samples obtained will be analyzed by cDNA microarray to determine if differences exist which can discriminate responding from non-responding tumors. However, if no significant activity is observed with ixabepilone in cervical cancer, it is unlikely that cDNA microarray, which entails a

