### 5.4 STATISTICAL SECTION

#### STUDY OBJECTIVES:

Primary: To establish the activity of ixabepilone administered daily as a one-hour infusion on five successive days (daily x 5), every three weeks in patients with cervical carcinoma previously treated with chemotherapy, as determined by overall response (PR+CR). Activity will be measured using standard RECIST guidelines.

Secondary: Assess pharmacodynamic endpoints after ixabepilone administration to determine the extent of tubulin polymerization and whether or not there has been activation of cellular death pathways “distal” to the target, and to estimate the progression free survival and duration of response.

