*cDNA Micro-array:* Biopsy material that will be used for micro-array analyses will be flash-frozen as soon as practically possible after obtaining the sample (< 20 minutes). The biopsy will be flash-frozen using either liquid nitrogen or a dry ice ethanol bath and then stored at -70 °C to -80 °C. Total RNA will be prepared from frozen biopsy tissue using RNeasy® Kits (Qiagen, Valencia, CA) following the manufactures instructions. Micro-arrays will be used to measure the steady state expression level of nearly all known human genes in the fresh-frozen biopsies. Approximately 3 - 10 mg of total RNA will be used to generate fluorescent-labeled cDNA for hybridization to the Human Genome U95 gene set (Affymetrix, Inc. Santa Clara CA). The complete Human U95 gene set contains 60,000 expression elements that represent approximately 12,000 full length genes and 50,000 ESTs.

Collection, handling, and storing of blood specimens for tubulin polymerization assay using PBMCs: (1) Collection: Blood samples are to be collected from an indwelling catheter or by direct venipuncture. Each blood sample should be collected into a pre-labeled 8 mL Becton-Dickinson CPT Vacutainer® tube. (2) Handling: Following blood collection, the tubes should be inverted several times to ensure mixing with the anticoagulant. Tubes should remain at room temperature and be centrifuged for 30 minutes at approximately 1700 x g at 20°C within 15 minutes of collection. The PBMCs should be transferred to a separate polypropylene tube and washed twice with 10 mL of ice-cold phosphate buffered saline (PBS). Following each washing, cells should be separated by centrifugation at 1700 x g for 10 minutes. Following the second washing, remove as much liquid as possible. The tube may be inverted on a paper towel for a few minutes to remove residual liquid, provided the cell pellet does not become dislodged from the tube bottom. (3) Storing: The PBMC cellular pellet should be stored at -70 to -80°C until

assayed. Samples should be labelled. Each label will have the study number, sample matrix, and nominal sample time. Once affixed on tubes, the labels should be wrapped completely by applying protective transparent tape for protection during handling, and storage. The actual time, as well as the date, for each sample should be recorded.

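### The tubulin staining endpoint is a judged pre/post comparison, and the plan has no step that hides time point or clinical response from the reader

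*Combined protocol and SAP*

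**What the plan says.** The secondary objective in section 5.4 is stated as: "Assess pharmacodynamic endpoints after ixabepilone administration to determine the extent of tubulin polymerization". It also covers activation of cell-death pathways. Section 1.2.5 (item 1) says how polymerization in malignant cells will be recognised: "as evidenced by enhanced staining with the acetylated alpha-tubulin and detyrosinated (glu-terminated) alpha-tubulin antibodies". The judgement is reached "by comparing the results in the post-treatment sample with those in the pre-treatment sample".

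On handling, Appendix A (Disposition of samples) says that "all specimens should be labeled with the patient's name, hospital number, date and time of collection". It continues: "Once the samples reach the laboratory they will be appropriately labeled and coded without names". The laboratory notebook holds the patient's name and ID number, the biopsy date, and "whether the sample is pre- or post-ixabepilone administration". For the blood samples (peripheral blood mononuclear cells, PBMCs), Appendix A adds: "Each label will have the study number, sample matrix, and nominal sample time".

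Appendix A automates the staining procedure but does not describe how slides are read. Independent review appears only in section 5.2, for tumor response.

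**The concern.** Whether a stain has become stronger is a judgement unless a scale or image measurement is specified, and neither is. A reader who knows which slide is post-treatment, and who expects an increase, can tilt borderline calls that way. The expectation is documented: section 1.2.5 reports rises in detyrosinated alpha-tubulin in 11 of 13 serial biopsies, and in acetylated alpha-tubulin in 11 of 12, from patients given ixabepilone in previous work.

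Two uses of the readings are exposed. Section 1.2.5 intends them to separate patients in whom the drug did not affect tubulin from those in whom it did but cell death did not follow. A false call of increased staining moves a patient from the first group to the second. Section 1.2.5 also wants to pursue whether baseline acetylated tubulin is higher in tumors that respond. For that question, knowledge of clinical response is the threat.

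**Working it through.** **Check of the text.** The protocol gives no sample size, test or decision rule for this endpoint, so there is no figure of its own to reproduce. The passages compare as follows.

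| Question | What the protocol provides |
|---|---|
| How is the endpoint read? | Stronger staining, post versus pre (1.2.5). No scale, threshold, second reader or image quantification |
| Is the time point on the sample? | Date and time on every specimen at collection; pre/post status in the notebook; nominal time on PBMC tubes (Appendix A) |
| What does laboratory coding remove? | Names. The rest of the code's content is not described |
| Are readers masked to time point or response? | Not stated |
| Is there independent review? | For tumor response only (5.2) |
| Is there a less subjective read-out? | Protein is isolated only if the sample is large enough (1.2.5, item 3); needle aspirates are processed for immunohistochemistry alone (3.4.1) |

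Immunohistochemistry is therefore the read-out most likely to be available for every biopsied patient, and it is also the most subjective. The PARP blots run pre and post samples in pairs with equal protein and a loading control, which narrows the room for judgement. No masking is stated there either.

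**Illustration of size.** The inputs below are assumptions, not protocol values.

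- n = 12 pairs with no true change.
- A group effect is called when at least 10 of the 12 are scored as increased.
- q is the chance that the reader scores a pair as increased.

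The false-positive rate is P(X ≥ 10) = 66·q¹⁰(1−q)² + 12·q¹¹(1−q) + q¹².

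- q = 0.5: (66 + 12 + 1)/4096 = 79/4096 = 0.019
- q = 0.6: 0.0639 + 0.0174 + 0.0022 = 0.083
- q = 0.7: 0.1678 + 0.0712 + 0.0138 = 0.253

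With 24 assumed pairs and a call at 17 or more, the same calculation gives 0.032, 0.192 and 0.565. More pairs do not cure a reader tilt; they make a false finding more likely.

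**The case against.** The strongest reply is that silence is not evidence of unmasked reading. Any paired study must record which sample is which, so the notebook is necessary and does not show that the slide reader consults it. Four stronger readings are tempting, and the documents do not support them.

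- **A reader might infer that slides are read unmasked by the laboratory that expects a rise.** No section says who scores them or what the laboratory code reveals. What stands is narrower: coding is described only as removing names, and no masking step is specified.
- **A reader might infer that the nominal time on PBMC tubes biases the staining.** It cannot. PBMCs are assayed as lysed pellets (3.4.3), not by immunostaining, and section 1.2.5 reports little or no change in them previously. The concern lies with the biopsies.
- **A reader might take the binomial figures as this trial's error rate.** The protocol has no such rule. The 10-of-12 threshold and the 60% and 70% tilts are assumed. The previous counts came from quantitative Western blots with changes of 2-fold or more, not from slide calls. If a reading of unchanged is allowed, the even-handed chance of an increase falls below 50% and the baseline shifts.
- **A reader might infer that knowing the time point distorts the baseline-predictor question.** Only knowledge of response could do that, and nothing shows that readers have it. Equally, nothing keeps it from them.

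There are also partial safeguards: comparison with normal cells in the same biopsy where present, a protein assay where tissue allows, automated staining, and loading controls on the PARP blots. They limit the problem. None of them masks the stain reading.

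**Conclusion.** The point holds as a minor, inexpensive improvement. The plan rests a secondary endpoint on a judged paired comparison and contains no step to keep time point or response from the reader. Followed as written, it leaves the staining result, and less so the blots, open to expectation bias. This rests on the absence of any masking provision combined with specimens that carry their collection date and time. It does not rest on any statement that reading is unmasked.

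The size cannot be determined from the documents; the false-positive rates above show direction only. The consequence is contained. Biopsies are optional (Appendix B), the activity decision in section 5.4.1 depends on RECIST response, and the microarray and isotype work is triggered by response rate rather than staining. The protocol itself treats the predictive observations as hypothesis-generating. What is at stake is the credibility of the explanation offered for treatment failure.

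**What to change.** Add a short paragraph to Appendix A, applying at the assay stage:

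1. Relabel biopsy slides, and lysates where blots are read, with a random code that shows neither time point nor clinical response.
2. Read them in random order on a score fixed in advance, stating the scale and what counts as an increase.
3. Lock the scores before the code is broken.
4. Have the key held by an existing staff member who does not read the samples, kept apart from the notebook that readers may use.

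Keep the collection labels, the nominal time on PBMC tubes and the tracking log unchanged. They are needed for traceability, and the PBMC label also guards against confusing samples drawn at different hours.

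The score definition should name the antibodies it applies to. Section 1.2.5 relies on acetylated and detyrosinated alpha-tubulin, while the immunostaining paragraph of Appendix A lists only a p53 antibody and a monoclonal anti-alpha-tubulin (DM1A). The two should be reconciled.

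The cost is a modest amount of relabelling and decoding by existing staff, with a slight added risk of sample mix-up that a check against the log can contain. No extra biopsy, assay or patient visit is needed. If masked, coded reading is already laboratory practice, a sentence describing it would settle the masking point.

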#### Guidelines for reporting loss or destruction to IRB:

The PI will report any loss or destruction of samples to the IRB. Any new use of the samples, specimens, or data outside of this protocol will require prospective IRB review and approval.

APPENDIX B: Study Calendar

EVALUATIONS REQUIRED PRE, DURING, AND POST THERAPY:

	A	B	C	D	E	F
Complete medical history		X				
Interim medical history				X		X
Physical examination		X		X		X
Weight and height		X		X		
Vital signs		X		X		X
ECOG performance status	X	X		X		X
Urine pregnancy test		X				
HIV Screen/Hepatitis B and C Screen	X					
Staging laboratory evaluation		X			X	X
Routine laboratory evaluation		X		X		X
CBC with differential and platelet count		X	X	X		X
Staging imaging studies	X				X	X
Biopsy & Research bloods (if indicated)*				✗		✗

A: Within 4 weeks prior to initiating therapy

B: Within 1 week prior to initiating therapy

C: Weekly or twice weekly during period of anticipated neutropenia

D: Every cycle

E: Every 2 cycles (Imaging studies and chest radiograph every third cycle after cycle 6)

F: Study termination.

\*Biopsies will be obtained after consent but before Day 1 dosing, and again on either Day 4 or Day 5. Biopsies are optional.

Research Labs for tubulin polymerization will be obtained prior to the Cycle 1 Day 1 drug infusion, and 1, 8 and 24 hours after Day 1 infusion start, and on either Day 4 or 5, within 1 hour of the biopsy. The research labs will only be done in those patients who have biopsies performed.

APPENDIX C: List of drugs that may have potential CYP3A4 interactions

(source: ctep.cancer.gov) [Updated on May 1, 2007]

When drugs classified as 'substrates' are co-administered with BMS-247550 there is the potential for higher concentrations of the 'substrate'. When BMS-247550 is co-administered with compounds classified as 'inhibitors', increased plasma concentrations of BMS-247550 is the potential outcome. The co-administration of 'inducers' would potentially lower plasma BMS-247550 concentrations. Only major substrates and effective inducers are listed.

**List of drugs that may have potential CYP3A4 interactions**

**CYP3A4 Substrates**

Albuterol	Dihydroergotamine	Isradipine	Quinidine
Alfentanil	Diltiazem	Itraconazole	Rabeprazole
Alprazolam	Disopyramide	Ketamine	Ranolazine
Amiodarone	Docetaxel	Ketoconazole	Repaglinide
Amlodipine	Doxepin	Lansoprazole	Rifabutin
Amprenavir	Doxorubicin	Letrozole	Ritonavir
Aprepitant	Doxycycline	Levonorgestrel	Salmeterol
Aripiprazole	Efavirenz	Lidocaine	Saquinavir
Atazanavir	Eletriptan	Losartan	Sibutramine
Atorvastatin	Enalapril	Lovastatin	Sildenafil
Benzphetamine	Eplerenone	Medroxyprogesterone	Simvastatin
Bisoprolol	Ergoloid mesylates	Mefloquine	Sirolimus
Bortezomib	Ergonovine	Mestranol	Spiramycin
Bosentan	Ergotamine	Methadone	Sufentanil
Bromazepam	Erythromycin	Methylethylgonovine	Sunitinib
Bromocriptine	Escitalopram	Methysergide	Tacrolimus
Budesonide	Estradiol	Miconazole	Tamoxifen
Buprenorphine	Estrogens, conj., synthetic	Midazolam	Tamsulosin
Buspiron	Estrogens, conj., equine	Miglustat	Telithromycin
Busulfan	Estrogens, conj., esterified	Mirtazapine	Teniposide
Carbamazepine	Estrone	Modafinil	Tetracycline
Cerivastatin	Estropipate	Montelukast	Theophylline
Chlordiazepoxide	Ethinyl estradiol	Moricizine	Tiagabine
Chloroquine	Ethosuximide	Nateglinide	Ticlopidine
Chlorpheniramine	Etoposide	Nefazodone	Tipranavir
Cilostazol	Exemestane	Nelfinavir	Tolterodine
Cisapride	Felbamate	Nevirapine	Toremifene
Citalopram	Felodipine	Nicardipine	Trazodone
Clarithromycin	Fentanyl	Nifedipine	Triazolam
Clobazam	Flurazepam	Nimodipine	Trimethoprim
Clonazepam	Flutamide	Nisoldipine	Trimipramine
Clorazepate	Fluticasone	Norethindrone	Troleandomycin
Cocaine	Fosamprenavir	Norgestrel	Vardenafil
Colchicine	Gefitinib	Ondansetron	Venlafaxine
Conivaptan	Haloperidol	Paclitaxel	Verapamil
Cyclophosphamide	Ifosfamide	Pergolide	Vinblastine
Cyclosporine	Imatinib	Phencyclidine	Vincristine
Dantrolene	Indinavir	Pimozide	Vinorelbine
Dapsone	Irinotecan	Pipotiazine	Zolpidem
Dasatinib (1)	Isosorbide	Primaquine	Zonisamide
Delavirdine	Isosorbide dinitrate	Progesterone	Zopiclone
Diazepam	Isosorbide mononitrate	Quetiapine	

### CYP3A4 Inhibitors

Acetaminophen	Diclofenac	Lomustine	Primaquine
Acetazolamide	Dihydroergotamine	Losartan	Progesterone
Amiodarone	Diltiazem	Lovastatin	Propofol
Amlodipine	Disulfiram	Mefloquine	Propoxyphene
Amprenavir	Docetaxel	Mestranol	Quinidine
Anastrozole	Doxorubicin	Methadone	Quinine
Aprepitant	Doxycycline	Methimazole	Quinupristin
Atazanavir	Drospirenone	Methoxsalen	Rabeprazole
Atorvastatin	Efavirenz	Methylprednisolone	Ranolazine
Azelastine	Enoxacin	Metronidazole	Risperidone
Azithromycin	Entacapone	Miconazole	Ritonavir
Betamethasone	Ergotamine	Midazolam	Saquinavir
Bortezomib	Erythromycin	Mifepristone	Selegiline
Bromocriptine	Ethinyl estradiol	Mirtazapine	Sertraline
Caffeine	Etoposide	Mitoxantrone	Sildenafil
Cerivastatin	Felodipine	Modafinil	Sirolimus
Chloramphenicol	Fentanyl	Nefazodone	Sulconazole
Chlorzoxazone	Fluconazole	Nelfinavir	Tacrolimus
Cimetidine	Fluoxetine	Nevirapine	Tamoxifen
Ciprofloxacin	Fluvastatin	Nicardipine	Telithromycin
Cisapride	Fluvoxamine	Nifedipine	Teniposide
Clarithromycin	Fosamprenavir	Nisoldipine	Testosterone
Clemastine	Glyburide	Nizatidine	Tetracycline
Clofazimine	Grapefruit juice (2)	Norfloracin	Ticlopidine
Clotrimazole	Haloperidol	Olanzapine	Tranylcypromine
Clozapine	Hydralazine	Omeprazole	Trazodone
Cocaine	Ifosfamide	Orphenadrine	Troleandomycin
Conivaptan	Imatinib	Oxybutynin	Valproic acid
Cyclophosphamide	Indinavir	Paroxetine	Venlafaxine
Cyclosporine	Irbesartan	Pentamidine	Verapamil
Danazol	Isoniazid	Pergolide	Vinblastine
Dasatinib (1)	Isradipine	Phencyclidine	Vincristine
Delavirdine	Itraconazole	Pilocarpine	Vinorelbine
Desipramine	Ketoconazole	Pimozide	Voriconazole
Dexmedetomidine	Lansoprazole	Pravastatin	Zafirlukast
Diazepam	Lidocaine	Prednisolone	Ziprasidone

### CYP3A4 Inducers

Aminoglutethimide	Nevirapine	Phenytoin	Rifapentine
Carbamazepine	Oxcarbazepine	Primidone	St. John's wort (3)
Fosphenytoin	Pentobarbital	Rifabutin	
Nafcillin	Phenobarbital	Rifampin	

When drugs classified as 'substrates' are co-administered with (*Study Agent*), there is the potential for higher concentrations of the 'substrate'. When (*Study Agent*) is co-administered with compounds classified as 'inhibitors', increased plasma concentrations of (*Study Agent*) is the potential outcome. The co-administration of 'inducers' would potentially lower plasma (*Study Agent*) concentrations.

Note: Adapted from Cytochrome P450 Enzymes: Substrates, Inhibitors, and Inducers. In: Lacy CF, Armstrong LL, Goldman MP, Lance LL eds. Drug Information Handbook 15TH ed. Hudson, OH; LexiComp Inc. 2007: 1899-1912.

Only major substrates and effective inducers are listed.

Additional information for drug interactions with cytochrome P450 isoenzymes can be found at <http://medicine.iupui.edu/flockhart/>.

(1) Investigator's Brochure: Dasatinib (BMS 354825). Bristol-Myers Squibb. October 2006.

(2) Malhotra *et al.* (2001). Clin Pharmacol Ther. 69:14-23.

(3) Mathijssen *et al.* (2002). J Natl Cancer Inst. 94:1247-1249.  
 Frye *et al.* (2004). Clin Pharmacol Ther. 76:323-329.

